### 3.1.2 Criteria to Proceed with a New Cycle of Therapy during Induction

Given that patients entering the trial may have baseline cytopenias due to their underlying disease, the criteria to initiate a new cycle of therapy will largely be a reflection of resolution of drug induced myelosuppression despite a possible background level of disease related myelosuppression.

For the phase I patients: subjects may start a new cycle or cycle 1 day 1 when the ANC is greater than 800/mm^3 and the platelet count is greater than 30,000/mm^3. In addition, non-hematologic toxicities must have recovered as described in Section 8. If a patient does not meet the criteria to initiate cycle 1 day 1 because of cytopenias encountered in the loading phase, the patient may be allowed to proceed with cycle 1 day 1 with growth factor or transfusion support after discussion between the treating physician and principal

investigator, however the patient will not be considered evaluable for DLT and will be replaced during the phase I.

Any other drug-related adverse events that may have occurred have resolved to  $\leq$  grade 2 severity.

For the phase II patients: For patients with baseline (at the time of eligibility) grade 3 thrombocytopenia or neutropenia, a new cycle of therapy (or cycle 1 day 1) can be started when the ANC is greater than  $800/\text{mm}^3$  and the platelet count is than  $30,000/\text{mm}^3$ . In addition, non-hematologic toxicities must have recovered as described in Section 6.1. For example, if a patient initial platelet count was  $40,000/\text{mm}^3$ , the patient may be able to restart another cycle on day 1 if his/her platelet count is greater than  $30,000/\text{mm}^3$ .

For patients without baseline grade 3 thrombocytopenia or neutropenia, a new cycle of therapy (or cycle 1 day 1) can be initiated when the ANC is greater than  $800/\text{mm}^3$  and the platelet count is greater than  $50,000/\text{mm}^3$ . In addition, non-hematologic toxicities must have recovered as described in Section 6.1

For patients who do not meet criteria to start cycle 1 day 1 because of hematologic adverse events encountered during the loading phase, patients may be allowed to proceed with cycle 1 after discussion between the treating physician and principal investigator provided the patient will receive growth factor and /or transfusion support during cycle 1.

Any other drug-related adverse events that may have occurred have resolved to  $\leq$  grade 2 severity.

If these conditions are not met on Day 1 of a new cycle, the subject will be evaluated weekly and a new cycle of treatment will not be initiated until the toxicity has resolved as described above. If study drug dosing was halted during the previous cycle and was restarted with a one-level dose reduction without requiring an interruption for the remainder of the cycle, then that reduced dose level will be initiated on Day 1 of the new cycle. **If study drug dosing was omitted for the remainder of the previous cycle or if the new cycle is delayed due to toxicity newly encountered on the scheduled Day 1**, then the new cycle will be started with a one-level dose reduction of the causative agent.

If recovery from toxicities is prolonged beyond 7 days, then the dose of selinexor, Liposomal doxorubicin or dexamethasone will be decreased by one dose level depending on which agent is felt to be the causative factor or more likely contributing factor.

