### **6.1 Study Assessments**

#### **6.1.1 Efficacy Assessments**

The clinical activity of selinexor will be evaluated for its effects on disease response criteria in terms of best response, duration of response, progression-free survival (PFS) and overall survival (OS). Disease status will be measured by the uniform response assessment of the International Myeloma Working Group.

The baseline disease assessment must be recorded and measured within 28 days prior to treatment start. During the treatment period, disease assessments will be performed every cycle, and as clinically indicated.

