Grade 1 (ANC < LLN - 1500/mm  ) Grade 2 (ANC < 1500 - 1000/mm  ) Grade 3 (ANC < 1000 - 500/mm  )	Maintain dose level The use of growth factors during selinexor treatment is permitted during the phase II and after cycle 1 is completed in the phase I.
Grade 4 (ANC < 500/mm  )	Hold study treatment until ANC returns to >800/mm  . Dose reduce LD (if appropriate) and consider growth factor support.
Febrile neutropenia, or fever of unknown origin without clinically or microbiologically documented infection (ANC < 1.0 x 10  /L, fever $\geq$ 38.5°C)	Hold study treatment until patient has stabilized. Dose reduce LD (if appropriate) and consider a dose reduction in selinexor
Thrombocytopenia (Platelets) (uncommon)	
Grade 1 (PLT < LLN - 75,000/mm  ) Grade 2 (PLT < 75,000 - 50,000/mm  )	Maintain dose level.
Grade 3 (PLT < 50,000 -25,000/mm  ) without bleeding	Maintain dose level
Grade 4 (PLT < 25,000/mm  ) without bleeding	Delay study treatment until resolved to $\leq$ grade 3. Dose reduce LD (if appropriate) and / or selinexor Platelet transfusions may be given to support platelet levels in patients with clear clinical benefit from selinexor.
Grade $\geq 3$ with bleeding	Delay study treatment until resolved to $\leq$ grade 2, reduce dose by 1 level when resolved.
Hyponatremia (common)	
Grade 1 (Lower Limit of Normal to 130nM)	Maintain dose level, assure adequate fluid, electrolyte and caloric intake, adjust other medications, consider salt supplementation, rule out other causes.
Grade 3 (120-130nM)	Discontinue selinexor until resolved to grade $\leq 1$ then consider reducing dose by 1 level

	especially if another cause is not identified. Check renal function, serum and urinary electrolytes, and rule out other causes.
Diarrhea (uncommon)	
Grade 1 (despite maximal anti-diarrheal medication)	At the first sign of abdominal cramping, loose stools, or onset of diarrhea, it is recommended that the patient be treated according to institutional standard of care. Maintain dose level of selinexor.
Grade 2 (despite maximal anti-diarrheal medication)	Hold therapy. If diarrhea returns as $\geq$ Grade 2, then reduce selinexor dose by one dose level until resolved to $\leq$ grade 1
Grade 3/4 (despite maximal anti-diarrheal medication)	Delay selinexor until resolved to $\leq$ grade 2, then follow guidelines above.
Other adverse events	

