Grade 3 (blistering, ulceration, or swelling interfering with walking or normal daily activities; cannot wear regular clothing) Grade 4 (diffuse or local process causing infectious complications, or a bed ridden state or hospitalization)	Delay dosing up to 2 weeks or until resolved to Grade 0-1. Decrease Liposomal doxorubicin by 1 dose level and return to original dose interval. If after 2 weeks there is no resolution, Liposomal doxorubicin should be discontinued.
Neutropenia	
Grade 1, 2, 3	Maintain dose level. Growth factor support is permitted during the phase II portion and the

	phase I after cycle 1.
Grade 4	Hold study treatment until ANC returns to >800/mm  . Reduce Liposomal doxorubicin by 1 dose level. Recommend growth factor support if not already implemented
Febrile Neutropenia	Hold study treatment until patient has stabilized. Dose reduce LD by 1 dose level and recommended growth factor support
Thrombocytopenia	
Grade 1,2,3 without bleeding	Maintain dose level
Grade 4 or grade 3 with clinical bleeding	Delay study treatment until resolved to thrombocytopenia is resolved to grade 3 or less and bleeding stopped. Reduce LD by 1 dose level. Platelet transfusion are allowed per routine clinical care
Serum Bilirubin (when not related to Gilbert's Syndrome)	
1.2 – 3.0 mg/dL	Reduce LD by 25%
> 3 mg/dL	Reduce LD by 50%
Cardiac Toxicities	
Arrhythmia ≥ grade 2	Hold Liposomal doxorubicin until resolved to ≤ grade 1. Decrease Liposomal doxorubicin by 1 dose level
Arrhythmia ≥ grade 3	Discontinue Liposomal doxorubicin. Patients may continue on selinexor if there is a clinical benefit in the opinion of the investigator
Congestive heart failure ≥ grade 2	Discontinue Liposomal doxorubicin. Patients may continue on selinexor if there is a clinical benefit in the opinion of the investigator
Asymptomatic decrease in ejection fraction by 20% or more	Discontinue Liposomal doxorubicin
Other non-hematologic Adverse Events	
Grade 1, 2	Maintain dose level and initiate standard supportive care
Grade 3	Delay dose until resolved to grade 1 or less, then reduce by 1 dose level
Grade 4	Discontinue Liposomal doxorubicin

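### Three cycle-start rules refer to Section 6.1, which has no recovery criteria, and the grade 2 rule in Section 3.1.2 disagrees with some rows of Tables 2–4

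*Combined protocol and SAP*

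**What the plan says.** Section 3.1.2 sets the conditions for starting an induction cycle. For phase I it states: "In addition, non-hematologic toxicities must have recovered as described in Section 8". For phase II it gives two hematologic thresholds, according to baseline cytopenia, and after each says that "non-hematologic toxicities must have recovered as described in Section 6.1". Both the phase I and the phase II text then add a residual condition: "Any other drug-related adverse events that may have occurred have resolved to" grade 2 or lower. Section 3.1.3 (maintenance) gives neutrophil and platelet minima, refers to Section 6.1 in the same words, and states no grade.

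Section 6.1 is headed Study Assessments. It opens with efficacy ("The clinical activity of selinexor will be evaluated for its effects on disease response criteria") and continues with translational work, safety monitoring, the DLT definition and laboratory tests.

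The restart thresholds are in Section 8: Table 2 (selinexor), Table 3 (liposomal doxorubicin, LD) and Table 4 (dexamethasone). The catch-all non-hematologic rows of Tables 3 and 4 read "Delay dose until resolved to grade 1 or less, then reduce by 1 dose level", for grade 3 in Table 3 and grades 3 and 4 in Table 4. Table 2 has the same threshold for other grade 3 events.

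For grade 3 thrombocytopenia with bleeding, Table 2 delays study treatment to grade 2 or lower and says "reduce dose by 1 level when resolved". Table 3 delays study treatment until "thrombocytopenia is resolved to grade 3 or less and bleeding stopped". For grade 3/4 diarrhea, Table 2 delays selinexor to grade 2 or lower, "then follow guidelines above".

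**The concern.** Whether a patient may be dosed on Day 1 should follow from one rule that every site can find. Here the phase II and maintenance references lead to a section with nothing to apply, and where a grade is stated it depends on which passage is opened.

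The consequences are operative. Under 3.1.2, a cycle whose conditions are not met waits for weekly re-evaluation. A delay for toxicity newly seen on Day 1 brings a one-level reduction of the causative agent, and recovery taking longer than 7 days also brings a reduction. Section 8.1.3 takes a patient off protocol treatment after a drug-related delay of more than 4 weeks, and the notes to Table 2 discontinue after an interruption of more than 28 days. Table 3 stops LD if stomatitis or hand-foot syndrome of grade 2 or higher has not resolved after 2 weeks. The threshold therefore affects dose intensity, delays and possibly removals. Three centers take part (Section 3.1), so readings may also differ by site.

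**Working it through.** No arithmetic applies; the check is a reading of 3.1.1–3.1.3, all of Section 6.1, and Tables 2–4 row by row.

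**Step 1: the references.** Sections 6.1.1 to 6.1.5 were read for any statement of when toxicity counts as recovered. Section 6.1.3 covers monitoring and CTCAE grading, and 6.1.4 defines DLTs; neither says when a cycle may start. The three references (two in 3.1.2, one in 3.1.3) have no content behind them. The phase I reference to Section 8 does.

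**Step 2: the grade 2 rule in 3.1.2 against the non-hematologic rows of Section 8.**

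| Row | Restart threshold | Against grade 2 or lower in 3.1.2 |
|---|---|---|
| Table 2, fatigue, grade 3 | grade 2 or lower | agrees |
| Table 2, anorexia, grade 3 or higher | grade 2 or lower | agrees |
| Table 2, nausea/emesis, grade 3 | grade 2 or lower | agrees |
| Table 2, diarrhea, grade 3/4 | grade 2 or lower, then back to the rows above | unclear |
| Table 2, hyponatremia, grade 3 | grade 1 or lower | differs |
| Table 2, other events, grade 3 | grade 1 or lower | differs |
| Table 3, stomatitis, grades 2 and 3–4 | grade 0–1 | differs |
| Table 3, hand-foot syndrome, grades 2 and 3–4 | grade 0–1 | differs |
| Table 3, other non-hematologic, grade 3 | grade 1 or lower | differs |
| Table 4, other non-hematologic, grade 3/4 | grade 1 or lower | differs |
| Table 4, dyspepsia/ulcer, edema, hyperglycemia | no grade stated | no comparison |

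A grade 3 event in a catch-all row that stands at grade 2 on Day 1 meets the residual condition of 3.1.2 and fails the row in Section 8. For stomatitis and hand-foot syndrome, the difference already arises when the event peaks at grade 2. For hyponatremia the stated thresholds differ, but Table 2's grade 1 and grade 3 bands meet at 130 and leave no grade 2 range, so the practical effect there is probably small.

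**Step 3: thrombocytopenia with bleeding.** Both tables delay study treatment as a whole, so the difference cannot be put down to one row covering selinexor and the other LD. Table 2 places grade 3 below 50,000 and down to 25,000/mm³. With bleeding stopped and platelets in that range, Table 3's condition is met and Table 2's is not. On Day 1 the platelet minima in 3.1.2 narrow this. Phase II patients without baseline grade 3 cytopenia need more than 50,000/mm³, so Table 3's looser grade cannot start their cycle. Where the minimum is 30,000/mm³ (phase I, and phase II with baseline grade 3 cytopenia), counts between 30,000 and 50,000/mm³ remain in dispute. Within a cycle, 3.1.2 does not settle it.

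**Step 4: diarrhea.** After grade 3/4 the event must fall to grade 2 or lower, and the reader is then sent to the rows above, where grade 2 says hold and grade 1 says keep the dose. Taken in sequence this can be followed, but it does not say plainly whether selinexor may restart at grade 2.

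**The case against.** The strongest reply is that Section 8 applies to everyone. The Study Schema text in 3.1.1 allows delays for toxicity under Section 8 without restricting this to phase I, and the neutropenia rows of Tables 2 and 3 address both phases. The references to 6.1 are then clerical errors with an obvious target. The conditions in 3.1.2 can also be read as cumulative, so that the stricter Section 8 rule prevails and the grade 2 sentence is only residual. Finally, Section 8 delays are largely specific to one agent, whereas 3.1.2 concerns the cycle.

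Much of this stands, and it rules out four stronger readings that a reader might infer:

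- That Tables 2–4 demand grade 1 or lower after every grade 3 event. They do not: three Table 2 rows use grade 2 or lower, and several Table 4 rows state no grade.
- That grade 2 is the only number in force for phase II and maintenance. Section 8 still applies, and 3.1.3 has no grade 2 rule at all.
- That the phase I and phase II patients combined in the 29 follow different recovery rules. The grade 2 sentence is the same for both phases and Section 8 is not limited to phase I; only the cited section differs.
- That the diarrhea rows contradict each other outright. They can be read in sequence.

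The reply does not remove the core. An evident intended target does not correct three wrong references. The residual reading does not separate the rules either, because the catch-all rows of Section 8 are themselves residual and cover the same events. Nothing in 3.1.2 says that the stricter rule prevails, or whether a cycle may start with one agent held.

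**Conclusion.** The concern holds in a limited form. Three cycle-start references lead to a section with no recovery rule. The grade 2 condition in 3.1.2 differs by one grade from the catch-all rows of Tables 2–4 and from the hyponatremia, stomatitis and hand-foot rows; it agrees with the fatigue, anorexia and nausea/emesis rows. Tables 2 and 3 differ by one grade on restarting study treatment after grade 3 thrombocytopenia with bleeding. The diarrhea wording needs clarifying but is not a proven contradiction.

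The number of patients affected is unknown, since the documents give no rate for events that have partly recovered by Day 1. No sample size, power or alpha figure depends on the point, and a bias in the pooled phase II response analysis is not shown. What is at stake is consistent dosing, delay and removal across patients and sites. The conclusion assumes that Section 8 is meant to apply in both phases and in maintenance, as 3.1.1 suggests. It takes no view on which threshold is right.

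**What to change.** In an amendment:

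1. Replace the two references to Section 6.1 in 3.1.2 and the one in 3.1.3 with the section that holds the recovery rules.
2. State whether 3.1.2 or Tables 2–4 governs Day 1 where they differ.
3. Reconcile the rows of Tables 2 and 3 for grade 3 thrombocytopenia with bleeding.
4. Reword the grade 3/4 diarrhea row so that its reference back to earlier rows has one meaning.

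The investigators should choose the thresholds; none is proposed here. The cost is amendment wording only, with no change to the design, the endpoints or the number of patients.

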### 8.2.4 Dose Adjustment Guidelines for Liposomal doxorubicin

**Table 3:** Guideline for the management of Liposomal doxorubicin toxicities

Toxicity and Intensity	Dose Modification
Stomatitis	
Grade 1 (painless ulcers, erythema, or mild soreness)	Redose unless patient has experienced previous Grade 3 or 4 toxicity. If so, delay up to 2 weeks and re-dose at the prior dose
Grade 2 (painful erythema, edema, or ulcers, but can eat)	Delay dosing up to 2 weeks or until resolved to Grade 0-1. If after 2 weeks there is no resolution, Liposomal doxorubicin should be discontinued. If resolved to Grade 0-1 within 2 weeks, and there was no prior Grade 3-4 stomatitis, continue treatment at previous dose. If patient experienced previous Grade 3-4 toxicity, discontinue Liposomal doxorubicin
Grade 3 (painful erythema, edema, or ulcers, and cannot eat) Grade 4 (requires parenteral or enteral support)	Delay dosing up to 2 weeks or until resolved to Grade 0-1. Decrease Liposomal doxorubicin dose by 1 dose level and return to original dose interval. If after 2 weeks there is no resolution, Liposomal doxorubicin should be discontinued.
Hand Food Syndrome HFS (Palmar Plantar Dysesthesias)	
Grade 1 (mild erythema, swelling, or desquamation not interfering with daily activities)	Redose unless patient has experienced previous Grade 3 or 4 HFS. If so, delay up to 2 weeks and decrease DOXIL ® dose by 1 dose level.
Grade 2 (erythema, desquamation, or swelling interfering with, but not precluding normal physical activities; small blisters or ulcerations less than 2 cm in diameter.)	Delay dosing up to 2 weeks or until resolved to Grade 0-1. If after 2 weeks there is no resolution, Liposomal doxorubicin should be discontinued. If resolved to Grade 0-1 within 2 weeks, and there are no prior Grade 3-4 HFS, continue treatment at previous dose and dose interval. If patient experienced previous Grade 3-4 toxicity, continue treatment with a decrease in 1 dose level

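### After a delayed cycle start, Section 3.1.2 reduces the dose where Tables 2 and 3 keep it for some of the same toxicities, and nothing says which text governs

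*Combined protocol and SAP*

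**What the plan says.** Section 3.1.2 sets count limits for starting a cycle. Phase I patients need an ANC above 800/mm³ and platelets above 30,000/mm³. The same limits apply to phase II patients who had grade 3 cytopenia at baseline. For the rest of phase II, "For patients without baseline grade 3 thrombocytopenia or neutropenia, a new cycle of therapy (or cycle 1 day 1) can be initiated when the ANC" exceeds 800/mm³ and platelets exceed 50,000/mm³.

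The section then has two sentences on dose after a delay. The first applies when dosing was omitted for the rest of the previous cycle, "or if the new cycle is delayed due to toxicity newly encountered on the scheduled Day 1"; in that case, "then the new cycle will be started with a one-level dose reduction of the causative agent". The second reads "If recovery from toxicities is prolonged beyond 7 days, then the dose of selinexor, Liposomal doxorubicin or dexamethasone will be decreased by one dose level", with the agent chosen by likely cause.

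The toxicity tables in Section 8 also govern dose:

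- Table 2 (selinexor) leaves the dose level unchanged for grade 1 to 3 neutropenia. It does the same in the row beginning "Grade 3 (PLT < 50,000 -25,000/mm", which is limited to patients without bleeding.
- Table 3 (LD) leaves the dose unchanged for grade 1 to 3 neutropenia and, for thrombocytopenia, in the row "Grade 1,2,3 without bleeding".
- Table 3 delays LD for Grade 2 hand-foot syndrome. If it resolves to Grade 0-1 within two weeks with no earlier Grade 3-4 episode, the instruction is to "continue treatment at previous dose and dose interval". The Grade 2 stomatitis row is similar.

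On recovery, Section 3.1.2 sends phase I patients to Section 8. For phase II it says "non-hematologic toxicities must have recovered as described in Section 6.1", and Section 3.1.3 gives the same reference for maintenance.

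**The concern.** A site that meets a low count or a Grade 2 mucosal or skin toxicity on Day 1 can follow Section 3.1.2 or the Section 8 table and give a different dose. No sentence ranks the two. The dose given after delays is part of the regimen behind the overall response rate in the 29 patients of the two-stage design, behind PFS, and behind the tolerability of the recommended phase II dose. If sites resolve the conflict differently, the response rate describes a mixture of reduction policies that the report could not specify. Patient safety is also involved, because the texts differ on the dose after a toxicity and, for some events, on how far the toxicity must resolve before treatment resumes.

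**Working it through.** No statistical figure is at issue, so the check compares the passages.

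**Inputs.** Start limits: Section 3.1.2. Grade bands and actions: Table 2 (Section 8.1.4) and Table 3 (Section 8.2.4). LD timing: Study Calendar footnote 17, which gives LD on Day 1 of cycles 1 to 8. Dose levels: Sections 8.1.3 and 8.2.3.

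**Step 1: counts too low to start, but with dose unchanged in the tables.** Take the grade 3 band and keep the part that fails the start limit.

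| Patients | Start limit | Grade 3 band | Overlap |
|---|---|---|---|
| All | ANC > 800 | 500 to < 1,000 | 500 to 800 |
| Phase I; phase II with baseline grade 3 cytopenia | Platelets > 30,000 | 25,000 to < 50,000 | 25,000 to 30,000 |
| Other phase II | Platelets > 50,000 | 25,000 to < 50,000 | 25,000 to < 50,000 (whole band) |

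The platelet rows apply without bleeding. In each overlap Section 3.1.2 delays the cycle. If the toxicity is new on Day 1 and attributed to a study drug, it reduces that drug by one level, while Tables 2 and 3 leave the dose alone. Example: a phase II patient with normal baseline counts has new, drug-related platelets of 40,000/mm³ without bleeding on Day 1 of cycle 3. The cycle is delayed, Section 3.1.2 reduces the causative agent, and both tables keep its dose.

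**Step 2: resolved Grade 2 stomatitis or hand-foot syndrome, no earlier Grade 3-4.**

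- Recovery in 8 to 14 days: Table 3 keeps the LD dose; the 7-day sentence reduces it.
- Recovery within 7 days, toxicity new on Day 1: Table 3 keeps the dose; the Day 1 sentence reduces it, provided that holding LD counts as delaying the cycle.

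**Step 3: where the texts agree.** For Grade 4 neutropenia or thrombocytopenia Table 3 also reduces LD, so there is no conflict on reducing that drug.

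**Step 4: the two sentences inside Section 3.1.2.**

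- New on Day 1, recovered by 7 days: the first reduces; the second is silent.
- New on Day 1, recovery beyond 7 days: both call for one level.
- Not new on Day 1, recovery beyond 7 days: the second applies; the first applies only if dosing had been omitted for the rest of the previous cycle.

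The sentences overlap, and what the second adds to the first is not stated.

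**Step 5: grade at restart.** Section 3.1.2 accepts other drug-related events at Grade 2 or lower. The residual rows of Tables 2 to 4 hold other Grade 3 events until Grade 1 or lower. For phase II and maintenance the pointer that might settle this leads to Section 6.1, Study Assessments. That section covers efficacy, translational, safety and laboratory assessments and the DLT definition, and has no recovery criteria.

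**Step 6: size of one level at dose level 2m, the stated recommended phase II dose.** Selinexor 80 to 60 mg: (80 − 60)/80 = 25%. LD 20 to 15 mg/m²: (20 − 15)/20 = 25%.

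**The case against.** The best defence is that the tables govern doses within a cycle and Section 3.1.2 governs cycle start. For selinexor, given on days 1, 8 and 15 at dose level 2m, that reading is possible. It fails for LD, which is given only on Day 1, so a Table 3 instruction on LD acts on the same dose that Section 3.1.2 governs. Table 3 also sets the LD dose after a delay, so it does not leave that question to Section 3.1.2.

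Several stronger readings are tempting, but the documents do not support them:

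- *Section 3.1.2 flatly contradicts itself.* The 7-day sentence does not say that a reduction follows only after 7 days. It gives a sufficient condition and can stand beside the other sentence. The fault is overlap and unclear purpose.
- *A long delay brings a two-level cut.* Each sentence gives one level, and neither calls its reduction additional.
- *Every Day 1 platelet count in the overlap is affected.* The toxicity must be newly encountered and have a causative agent. Section 3.1.2 itself recognises disease-related cytopenia.
- *The listed toxicity rates show that this is common.* The thrombocytopenia and hand-foot syndrome incidences in Section 8 have no breakdown by grade or by Day 1 timing, so they do not measure these events.
- *The different phase I and phase II platelet limits are an error.* They are set explicitly by phase and are a design choice.
- *Restart at Grade 2 is allowed in one place and barred in another across the board.* Table 2 itself permits restart at Grade 2 or lower after Grade 3 fatigue, anorexia or nausea. The mismatch concerns the residual category of other Grade 3 events. In phase I the reference to Section 8 may resolve it, with the Grade 2 clause read as a remainder.

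It is also fair that dose changes, delays and their reasons must be recorded in the CRF (Section 8.1.3), and that sites confer weekly in phase I and monthly in phase II (Section 14.3.2). This limits divergence but does not tell a site which text to follow.

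**Conclusion.** The plan gives conflicting instructions on dose after a delayed cycle start. For LD the conflict is clear in the count ranges of Step 1 and after resolved Grade 2 stomatitis or hand-foot syndrome; for selinexor it depends on whether Table 2 is read as applying at cycle start. The difference is one dose level, or 25% of the recommended phase II dose of the drug concerned. The two reduction sentences in Section 3.1.2 overlap, the restart grade for other Grade 3 events is unsettled, and the Section 6.1 references lead nowhere useful.

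This rests on the toxicity being new on Day 1 and attributed to a study drug or, for the 7-day sentence, on recovery taking more than 7 days. How often that happens, and what it does to the response rate, cannot be derived from the documents. A reader might infer that the two-stage design or its error rates are compromised; nothing here supports that, since no sample size, power or significance figure depends on these passages. The matter should be corrected because it bears on patient safety and on what regimen the response rate describes.

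**What to change.** Reconcile Section 3.1.2 with Tables 2 to 4, and state which text governs (a) the grade at which a cycle may restart and (b) the dose after a delayed start. Merge the two reduction sentences in Section 3.1.2 into one rule with non-overlapping conditions. Replace the references to Section 6.1 in Sections 3.1.2 and 3.1.3 with the section that holds the recovery criteria. Which clinical rule to adopt is for the investigators to decide.

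Optionally, summarise selinexor and LD dose intensity beside the overall response rate, so that readers can see what was delivered.

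The cost is a clarifying amendment with the usual review under Section 15.1 and, if wanted, one descriptive table from dosing data already recorded. No extra patients, visits or assessments are needed.
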